## 9 IMAGING METHODS

### 9.1 MR Imaging

#### 9.12 Methods

Anatomic imaging will be acquired with axial and coronal T2-weighted sequences. Motility will be evaluated using dynamic high spatial resolution 2D balanced steady state free precession (bSSFP) imaging. Coronal and axial balanced steady state images will be acquired during free breathing with an acquired temporal resolution of approximately 0.6s/image over 85 seconds. Diffusion weighted imaging will also be acquired using multiple b-values in order to evaluate any changes in diffusion restriction within the bowel wall or mesenteric lymph nodes between the two MRI exams.

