#### 9.13 Image Interpretation

**Anatomic imaging** will be assessed by a pediatric radiologist with expertise in abdominal imaging ([name]). The well-distended distal/terminal ileum bowel wall thickness will be measured in 3 locations, and a mean wall thickness value will be obtained on each exam. The largest visible right lower quadrant mesenteric lymph nodes will be measured in short axis on each exam. Any secondary signs of inflammation (perienteric fat stranding, engorged vasa recta, free fluid) will be documented on each exam. After completion of the primary anatomic review by [name], a second pediatric radiologist with expertise in abdominal imaging will perform the same review on a random subset of subjects in order to determine inter-reader reliability. The second reviewer will be blinded to the initial assessment as well as to the time point of imaging.

**Motility imaging** will be assessed as follows: First, a quantitative assessment will be performed. A well-distended segment of distal/terminal ileum will be chosen by the first reviewer ([name]). Novel, semi-automated software, will be utilized to assess the coronal cine sequences in this investigation. No pre-market submission to the FDA has been made for the software nor are there any current plans to do so in the future. The semi-automated method computes a cross sectional area across time and the creates a best fit curve to determine the frequency or frequencies of contraction. After reviewer 1 identifies the bowel segment of interest, a post processing assistant will draw a region of interest on the bowel lumen on every image of the sequence. The application then creates a map of luminal cross-sectional area over time. The area versus time waveforms can be submitted to secondary analysis from which contraction frequency and other quantitative metrics of interest can be extracted.

Next a qualitative assessment will be performed. The research assistant will create a movie file for each subject, randomize the timepoints, and then insert the movie file into a PowerPoint presentation. The two reviewers, along with a third reviewer (a pediatric gastroenterologist with expertise in gut motility) will review the images to determine which movie has faster motility, and for each movie, if the motility is organized or disorganized. Finally, each of the three reviewers will assess the focal segment of the distal/terminal ileum in the same manner.

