#### **a) Descriptive statistics:**

Descriptive statistics will be calculated for all demographic, anthropometric, reactogenicity, serum, image and fecal variables. For continuous variables, five-number (mean, SD, minimum, median, maximum) summaries will be produced. For class (categorical) variables, frequencies and percentages will be reported. Descriptive statistics will be calculated for the entire study population, as well as for each vaccine group at each time point. Investigators will be advised by study statisticians about potential outliers, or data entry issues, based on these summary statistics. To determine whether continuous serum, image and fecal outcomes meet the assumption of a Gaussian (normal) distribution, the Shapiro-Wilk test will be used. Where a significant departure from normality exists, an appropriate transformation of the data will be employed prior to inferential analyses. If transformations are not successful, non-parametric analyses will be used.

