**b) Inferential statistics**

The primary analysis for this study is the comparison of anatomical outcome as measured by MRI between (RV1, RV5 with and without other vaccines: 4 groups) and within (pre and post) study groups. The primary anatomical outcome will be the terminal ileum thickness measured in mm. The change in this outcome before and after vaccination will be compared for each study group (within group test) using a paired t-test, while the between group difference at pre, post and on the difference between pre and post (change score) will be initially analyzed using general linear model (GLM) where the ileum thickness (at pre, post and change score) is modeled as a function of group (4-groups). Depending on the result of the F-test from the GLM analysis, this will be followed by pairwise comparison between groups (6-comparisons). This will be examined using a two sample t-test. If the difference between groups with and without other vaccines for a given vaccine (RV1 or RV5) is not significant we might combine the categories and conduct a comparison test for the outcome between the two vaccine types. If the primary outcome is not normal before or after transformation we will use the non-parametric Kruskal-Wallis test to compare the groups. Although the primary between group comparisons is based on the pre-post change score, we are conducting additional analysis based on the pre and post data to get more insight about the distribution of the primary outcome variable.

We will also examine the distribution of socio-demographic and other potential covariates among the groups using a GLM analysis. If some covariates are differentially distributed among the groups, those covariates will be controlled for in the primary analysis described above. Potential modifiers such as breast milk or secretor status will be examined by modeling the primary outcome as a function of group, potential modifier and the interaction between group and modifier. In this case the parameter of interest is the coefficient of the interaction term, however it is possible that the interaction test might not be sensitive due to sample size. Regardless we will examine and report the observed change between groups for each potential modifier as a subgroup. For example we will report difference between groups in the primary outcome for secretors and non-secretors separately.

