To assess how vaccine shedding is related with the primary outcome by looking at the correlation between the imaging outcome and the fecal shedding for each group (using sample obtained close in time with the imaging). This will be examined using Pearson or Spearman correlation coefficients based on the normality of the data. The resulting correlation coefficient from each group can be compared with each other (pairwise) using Fisher's transformation and compare the resulting z-scores. If the correlation are not different we may then combine the groups and run the correlation across group to get an insight on the relationship between shedding and imaging parameter.

For all the other imaging parameters (cecum thickness, wave pattern and amplitude) similar analysis described for the primary outcome (ileum thickness) will be conducted. For Lymph node presence a logistic regression instead of GLM, and for the lymph node number, and wave frequency a Poisson regression will be used.

For the cytokines outcome (IL2, IL6, IL7, IL8, IL15, TNF) similar analysis described for the primary imaging outcome including examination of modifying variables and potential subsequent stratified analysis will be conducted.

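### Poisson regression is named for wave frequency, a curve-fitted value with no stated unit, so its standard error, CI and p-value depend on the time unit and ignore the observed spread

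*Combined protocol and SAP*

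**What the plan says.** Section 10.3 b) sets the pattern with the primary outcome, terminal ileum thickness. Within each arm, "The change in this outcome before and after vaccination will be compared for each study group (within group test) using a paired t-test". Between arms, a linear model is fitted to the pre, post and change values, and the change score has priority: "Although the primary between group comparisons is based on the pre-post change score". The plan then extends this: "For all the other imaging parameters (cecum thickness, wave pattern and amplitude) similar analysis" is to follow the primary outcome. It makes exceptions for lymph node presence (logistic regression) and for two further variables: "for the lymph node number, and wave frequency a Poisson regression will be used".

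Section 9.13 describes how frequency arises. The semi-automated software computes luminal cross-sectional area across time and "creates a best fit curve to determine the frequency or frequencies of contraction". The same section says that from the area-versus-time waveforms "contraction frequency and other quantitative metrics of interest can be extracted". Section 9.12 gives the only time base, "an acquired temporal resolution of approximately 0.6s/image over 85 seconds", and section 10.3 does not link it to the model.

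Section 10.3 a) provides a normality check for continuous image outcomes. If it fails, "an appropriate transformation of the data will be employed prior to inferential analyses", with non-parametric analysis as the last resort. Nothing comparable is given for the dispersion of a Poisson model.

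**The concern.** Poisson regression suits counts of events. It takes the variance to be equal to the mean, and it uses that assumption, not the data, to set the standard error. A frequency read off a fitted curve is a continuous measurement that can be written per second, per minute or per scan. Changing the unit multiplies the mean by a constant and the variance by the square of that constant, so the two can agree in at most one unit. The plan does not say which unit will be used.

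What is at stake is the precision reported for this outcome. The Power paragraph of section 10.3 makes effect sizes the product that future studies will draw on. The ratio and the descriptive SD would be sound, but the interval and p-value reported with the ratio would reflect the choice of unit and not the variation between infants.

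**Working it through.** **Inputs from the documents.** Up to 150 infants allocated 1:1:1:1 (section 4.1), so at most 150/4 = 37.5, taken as 37 per arm. The cine acquisition lasts 85 seconds (section 9.12). The plan has no power calculation and gives no mean, SD or unit for frequency, so there is no figure of its own to reproduce.

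**Assumptions, for illustration only.** Means of 8 and 9 contractions per minute in two arms; SD 1.2 or 2.4 per minute.

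**Step 1: the Poisson standard error in three units.** With dispersion fixed at 1,

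SE(log ratio) = sqrt(1/(n·m1) + 1/(n·m2)), and z = ln(m2/m1)/SE.

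ln(9/8) = 0.1178 in every unit. No SD appears in the formula.

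| Unit | m1, m2 | SE | z | p | Ratio (95% CI) |
|---|---|---|---|---|---|
| per minute | 8, 9 | 0.0799 | 1.474 | 0.14 | 1.125 (0.96 to 1.32) |
| per 85 s (×85/60) | 11.33, 12.75 | 0.0671 | 1.755 | 0.079 | 1.125 (0.99 to 1.28) |
| Hz (×1/60) | 0.133, 0.150 | 0.619 | 0.190 | 0.85 | 1.125 (0.33 to 3.78) |

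From per minute to Hz the SE grows by sqrt(60) = 7.7. Every row is the same at SD 1.2 and at SD 2.4.

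**Step 2: estimating the dispersion removes the dependence.** With equal SD s in both arms, the Pearson dispersion per minute is s²(1/8 + 1/9)/2, and the scaled z is the Poisson z divided by its square root.
- SD 1.2: dispersion 1.44 × 0.2361/2 = 0.17; z = 1.474/0.412 = 3.58; p = 0.0003.
- SD 2.4: dispersion 5.76 × 0.2361/2 = 0.68; z = 1.474/0.825 = 1.79; p = 0.074.

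The dispersion scales in proportion to the unit, so these p-values are identical in all three units. Robust standard errors give 0.0003 and 0.070.

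**Step 3: which way the error goes.** The Poisson SE divided by the true SE is (1/sqrt(mean))/CV, with the mean in the unit used. The test is too conservative when the CV is below 1/sqrt(mean) and anti-conservative above it. The crossover moves with both mean and unit:

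| Mean per minute | Crossover CV, per minute | Crossover CV, per 85 s |
|---|---|---|
| 4 | 50% | 42% |
| 6 | 41% | 34% |
| 8 | 35% | 30% |
| 12 | 29% | 24% |

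With four arms and no true difference, the Poisson statistic behaves approximately as mean × CV² times a chi-square on 3 df, so the nominal 5% test rejects with probability P(chi-square > 7.815/(mean × CV²)). Simulation at mean 8 per minute and 37 per arm gave:

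| CV | Per minute | Per 85 s |
|---|---|---|
| 10% | 0% | 0% |
| 20% | 0% | 0.1% |
| 30% | 1.4% | 5.4% |
| 37.5% | 7.3% | 17.9% |

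The F-test stayed at 4.9% to 5.1% throughout. At mean 12 per minute and CV 30%, per 85 s, mean × CV² = 17 × 0.09 = 1.53, and the probability that chi-square exceeds 7.815/1.53 = 5.11 is about 16%.

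**The case against.** The strongest reply is that wave frequency may mean a count of waves per scan. Section 10.3 b) groups it with lymph node number and apart from amplitude, and the scan lasts the same 85 seconds for every infant. On that reading the unit is fixed, no offset is needed, and Poisson is a reasonable starting model. This stands as far as it goes: the unit problem disappears. The dispersion problem remains, because nothing makes the variance of such a count equal its mean. The fitted-curve wording of section 9.13 favours a continuous value, but the documents do not settle the matter.

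It can also be said that leaving out robust or scaled errors is brevity, that motility is an exploratory objective (section 3.3), and that section 9.13 also plans a qualitative motility review. These points limit the importance of the problem without removing it.

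Three stronger readings are tempting and are not supported.
- A reader might infer that the pre-post change contrast and the within-arm test have no valid form for wave frequency or the node outcomes. Section 10.3 b) replaces only the between-arm model. It does not withdraw the paired t-test, which is valid for a continuous frequency. For counts and binary outcomes, a group-by-time term could supply a change contrast. The plan does not spell this out, but that is missing detail and not an impossibility.
- A reader might measure the loss by setting Poisson power against a t-test at one time point. The planned main contrast is the change score, whose SD is SD × sqrt(2(1 − r)), and the documents give no correlation r. For a 1-unit difference at 37 per arm, change-score power runs from 71% to 94% at SD 1.2 and from 24% to 42% at SD 2.4 as r goes from 0 to 0.5. A single-time-point comparison does not describe the gain from the fix.
- A reader might conclude that the main risk is lost power, or alternatively false positives. Step 3 shows either can occur, depending on a mean and SD that are not given.

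**Conclusion.** The concern holds for wave frequency. As written, the plan names a model whose interval and p-value are undefined until a unit is chosen, and which ignores the observed spread once it is. The square-root dependence on the unit is algebra and needs no assumption. The p-values of 0.14, 0.079 and 0.85 rest on the assumed means and on 37 per arm. The size and direction of the error in the actual data cannot be stated from the documents. The Hz row is the extreme case.

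The reach is limited. The ratio, the descriptive SD and the primary ileum-thickness analysis are unaffected, and the unit argument does not extend to lymph node number, which is a true count. The wording should be corrected before analysis, but the point does not threaten the trial's primary result.

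**What to change.** State the unit of wave frequency and whether it is a fitted value or a count of waves in the 85-second scan.
- **Fitted value:** analyse it as section 10.3 b) already analyses amplitude, with the linear model on the change score, the paired test within arm, and the transformation or non-parametric fallback of section 10.3 a).
- **Count per scan, with Poisson kept:** specify robust or Pearson-scaled standard errors.

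Optional clarification: say how the pre-post contrast is obtained for node number and node presence, for example by a Day 5 model with the baseline value as covariate.

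The cost is wording in the analysis plan, with no new data. On the linear scale the effect becomes a difference in the stated unit instead of a ratio. If the optional node models are adopted, their results would be baseline-adjusted Day 5 ratios and so on a different contrast from ileum thickness, which the plan should say.

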### **Power**

Since sample-sizes were predetermined and since this is a pilot study, no power calculations were conducted. Effect sizes will be reported from the results, to aid in the development of future studies.

### **Feasibility Analysis**

The proportion of children meeting the outlined feasibility benchmarks (Appendix 3) will be determined.

## **11 ASSESSMENT OF SAFETY**

### **11.1 Adverse Events**

RV1 and RV5 are recommended routinely for infants in the US and is consistent with normal standard of care. The risks associated with vaccination are not greater than those encountered in the performance of routine medical care.

#### **RV1 Adverse Events**

Anticipated common ( $\geq 5\%$ ) solicited adverse events related to the administration of the RV1 rotavirus vaccine include (as per Package Insert) fussiness/irritability, cough/runny nose, fever, loss of appetite, and vomiting. There is also a small risk for intussusception as shown in recent studies.

#### **RV5 Adverse Events**

Anticipated common adverse events related to the administration of the RV5 rotavirus vaccine include (as per Package Insert) include diarrhea, vomiting, irritability, otitis media, nasopharyngitis, and bronchospasm^116. There is also a small risk for intussusception as shown in recent studies.

Other vaccines – All vaccines used will be licensed and recommended for routine use by the ACIP.

Possible risks are explained in the Vaccine Information Statements.

(<http://www.cdc.gov/vaccines/hcp/vis/>).

Events meeting Vaccine Adverse Event Reporting System (VAERS) reporting requirements will be reported as indicated below.

As previously mentioned, there are minimal risks associated with venipuncture for obtaining research related labs. Foreseeable adverse events associated with venipuncture area: mild, temporary discomfort at the venipuncture site, bruising, and phlebitis.

#### **MRI /Ultrasound Adverse Events**

Subjects may have some discomfort due to the noise from the MRI scanner. Earplugs and headphones and/or MiniMuffs will be used to decrease sound levels to  $<+99\text{dB(dBA)}$ . Infants may

become fussy/irritable from being NPO 4 hours prior to the MRI (NPO three hours prior to visit and one hour for intake and preparation for the MRI).

Low density barium sulfate (VoLumen) will be used as an oral contrast agent for the MRI enterography. Barium sulfate is an inert substance and has an excellent safety profile with well over 60 years of use in patients. Barium is biologically inert and is not absorbed or metabolized by the body and is excreted unchanged. The risk of an allergic reaction is 1 in 1 million and the risk of a fatal reaction is 1 in 10 million (**Appendix 3**-Package Insert). There are no known risks from ultrasound.

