14. any condition which, in the opinion of the investigators, may post a health risk to the subject or interfere with the MRI or vaccine evaluation

15. currently receiving medication for gastroesophageal reflux (GERD) or any other gastrointestinal condition including colic
16. infant who is a relative of any research study personnel
17. allergy to barium
18. failed newborn hearing screening

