APPENDIX 3.  
VoLumen Package Insert

**DESCRIPTION:** VoLumen is a barium sulfate suspension 0.1% w/v, 0.1% w/w for oral administration. Each 100 mL contains 0.1 g barium sulfate. Barium sulfate, due to its high molecular density is opaque to x-rays and therefore, acts as a positive contrast agent for radiographic studies. The active ingredient is barium sulfate and its structural formula is BaSO4. Barium sulfate occurs as a fine, white, odorless, tasteless, bulky powder which is free from grittiness. Its aqueous suspensions are neutral to litmus. It is practically insoluble in water, solutions of acids and alkalis, and organic solvents. **Inactive Ingredients:** citric acid, natural gum, benzoic acid, sodium citrate, natural and artificial blueberry flavor, potassium sorbate, purified water, saccharin sodium, simethicone emulsion, sodium benzoate, and sorbitol.

**CLINICAL PHARMACOLOGY:** Barium sulfate, due to its high molecular density is opaque to x-rays and, therefore, acts as a positive contrast agent for radiographic studies. Barium sulfate is biologically inert and, therefore, is not absorbed or metabolized by the body, and is eliminated from the GI tract unchanged.

**INDICATIONS AND USAGE:** For use in Computed Tomography to opacify the GI tract.

**CONTRAINDICATIONS:** This product should not be used in patients with known or suspected gastrointestinal perforation or hypersensitivity to barium sulfate or any component of this barium sulfate formulation.

**WARNINGS:** Rarely, severe allergic reactions of an anaphylactoid nature, have been reported following administration of barium sulfate contrast agents. Appropriately trained personnel and facilities should be available for emergency treatment of severe reactions and should remain available for at least 30 to 60 minutes following administration, since delayed reactions can occur.

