**PRECAUTIONS: General:** Diagnostic procedures which involve the use of radiopaque contrast agents should be carried out under the direction of personnel with the requisite training and with a thorough knowledge of the particular procedure to be performed. A history of bronchial asthma, atopy, as evidenced by hay fever and eczema, or a previous reaction to a contrast agent, warrant special attention. Caution should be exercised with the use of radiopaque media in severely debilitated patients and in those with marked hypertension or advanced cardiac disease. Ingestion of barium is not recommended in patients with a history of food aspiration. If barium studies are required in these patients or in patients in whom integrity of the swallowing mechanism is unknown, proceed with caution. If barium is aspirated into the larynx, further administration should be immediately discontinued.

**Information for Patients:** Before administration of this product, patients receiving barium sulfate diagnostic agents should be instructed to:

1. Inform their physician if they are pregnant.
2. Inform their physician if they are allergic to any drugs or food, or if they have had any prior reactions to barium sulfate products or other contrast agents used in x-ray procedures (see **PRECAUTIONS-General**).
3. Inform their physician about any other medications they are currently taking.
4. Seek immediate medical attention if they experience an allergic reaction after using this product.

**Drug Interactions:** The presence of barium sulfate formulations in the GI tract may alter the absorption of therapeutic agents taken concomitantly. In order to minimize any potential change in absorption, the separate administration of barium sulfate from that of other agents should be considered.

**Usage in Pregnancy:** Radiation is known to cause harm to the unborn fetus exposed in utero. Therefore, radiographic procedures should only be used when, in the judgement of the physician, its use is deemed essential to the welfare of the pregnant patient.

**Nursing Mothers:** Barium sulfate products may be used during lactation.

TX1272-2

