**ADVERSE REACTIONS:** Adverse reactions, such as nausea, vomiting, diarrhea and abdominal cramping, accompanying the use of barium sulfate formulations are infrequent and usually mild. Severe reactions (approximately 1 in 1,000,000) and fatalities (approximately 1 in 10,000,000) have occurred. Procedural complications are rare, but may include aspiration pneumonitis, granuloma formation, intravasation, embolization and peritonitis following intestinal perforation, vasovagal and syncopal episodes, and fatalities.

**ALLERGIC REACTIONS:** Due to the increased likelihood of allergic reactions in atopic patients, it is important that a complete history of known and suspected allergies as well as allergic-like symptoms, e.g., rhinitis, bronchial asthma, eczema and urticaria, be obtained prior to any medical procedure utilizing these products. A mild allergic reaction would most likely include generalized pruritus, erythema or urticaria (approximately 1 in 250,000). Such reactions will generally respond to an antihistamine such as 50 mg of diphenhydramine or its equivalent. In the rarer, more serious reactions (approximately 1 in 1,000,000) laryngeal edema, bronchospasm or hypotension could develop. Severe reactions which may require emergency measures are often characterized by peripheral vasodilation, hypotension, reflex tachycardia, dyspnea, agitation, confusion and cyanosis, progressing to unconsciousness. Treatment should be initiated immediately with 0.3 to 0.5 cc of 1:1000 epinephrine subcutaneously. If bronchospasm predominates, 0.25 to 0.50 grams of intravenous aminophylline should be given slowly. Appropriate vasopressors might be required. Adrenocorticosteroids, even if given intravenously, exert no significant effect on the acute allergic reactions for a few hours. The administration of these agents should not be regarded as emergency measures for the treatment of allergic reactions. Apprehensive patients may develop weakness, pallor, tinnitus, diaphoresis and bradycardia following the administration of any diagnostic agent. Such reactions are usually non-allergic in nature and are best treated by having the patient lie flat for an additional 10 to 30 minutes under observation.

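### Sections 11.1 and 12 present the insert's rate for serious contrast reactions as the risk of any allergic reaction, and the contrast exclusion is worded more narrowly than the insert's contraindication

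*Combined protocol and SAP*

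**What the plan says.** Section 11.1, under MRI/Ultrasound Adverse Events, states: "The risk of an allergic reaction is 1 in 1 million and the risk of a fatal reaction is 1 in 10 million". It refers to the package insert reproduced as Appendix 3. The same sentence stands in Section 12, also with a reference to the insert. Neither place attaches a severity to the allergic reaction.

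Appendix 3 separates the rates by severity:

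- Adverse reactions: "Severe reactions (approximately 1 in 1,000,000) and fatalities (approximately 1 in 10,000,000) have occurred".
- Allergic reactions, mild: "A mild allergic reaction would most likely include generalized pruritus, erythema or urticaria (approximately 1 in 250,000".
- Allergic reactions, serious: "In the rarer, more serious reactions (approximately 1 in 1,000,000) laryngeal edema, bronchospasm or hypotension could develop".

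The insert's contraindication covers "known or suspected gastrointestinal perforation or hypersensitivity to barium sulfate or any component of this barium sulfate formulation". Its description lists inactive ingredients other than barium sulfate, among them benzoic acid, natural gum and sorbitol.

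Exclusion 17 in Section 4.3 reads "allergy to barium". Withdrawal reason 8 in Section 4.4 is likewise limited to barium.

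**The concern.** A statement about the risk of an allergic reaction, with no qualifier, covers mild and serious reactions alike. The figure given for it is the one that the insert keeps for the serious class, and the more frequent mild class has dropped out. The contrast is given for research imaging to healthy infants, and Section 12 expects no direct benefit to them, so a risk figure that cites a source should agree with that source.

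The eligibility wording raises a second, separate matter. An infant with known hypersensitivity to an ingredient other than barium falls within the insert's contraindication but not within exclusion 17 as written. What is at stake is the accuracy of a safety statement and the agreement of a safety exclusion with the protocol's own appendix. The trial's estimates are not involved.

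**Working it through.** **Inputs**

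- Protocol rate for an allergic reaction: 1 in 1,000,000 (Sections 11.1 and 12).
- Insert rate, mild allergic: about 1 in 250,000 (Appendix 3).
- Insert rate, more serious allergic: about 1 in 1,000,000 (Appendix 3).
- Insert rate, fatal: about 1 in 10,000,000 (Appendix 3).
- Infants: up to 150 (Section 4.1).
- Contrast feeds per infant: 2, taking one feed before each MRI, at Visits 1 and 2 (Section 6.6).

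**Where the protocol's figures come from**

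- Allergic: protocol rate / insert serious rate = (1/1,000,000) / (1/1,000,000) = 1.0.
- Fatal: protocol rate / insert fatal rate = (1/10,000,000) / (1/10,000,000) = 1.0.

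The protocol's pair is the insert's pair for severe and fatal reactions, without the word that marks the first as severe.

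**Any-severity allergic rate from the insert**

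- Mild alone: 1/250,000 = 4 per million. Ratio to the protocol: 4/1 = 4.
- Mild plus serious, counted as separate events: 4 + 1 = 5 per million, or 1 in 200,000. Ratio to the protocol: 5/1 = 5.

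**Expected number of allergic reactions in the trial**

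The insert does not say whether its rates are per exposure or per patient, so both readings are shown. Maximum feeds: 150 × 2 = 300.

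| Rate used | Per exposure (300) | Per patient (150) |
|---|---|---|
| Protocol, 1 per million | 0.0003 | 0.00015 |
| Insert, mild, 4 per million | 0.0012 | 0.0006 |
| Insert, mild plus serious, 5 per million | 0.0015 | 0.00075 |

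The ratio of 4 to 5 is the same on either reading. The absolute count is about 0.001 per exposure and smaller per patient.

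**Exclusion against contraindication**

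No arithmetic applies. The insert's hypersensitivity contraindication has two parts, barium sulfate and any other component. Exclusion 17 and withdrawal reason 8 state the first part only. No other item in Section 4.3 names hypersensitivity to a contrast component. Inclusion 2 (no obvious health problem) is general, and exclusion 14 depends on the investigators' opinion.

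**The case against.** The strongest reply is that this is one dropped word. The protocol's pair of figures follows the insert's sentence on severe reactions and fatalities, and adding a severity qualifier would make it correct. What is missing is mild reactions such as itching or urticaria, and the expected count stays near zero either way. All of that stands, and it limits the weight of the point. It does not make the sentence right as printed.

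The second reply is that exclusion 17 is not the whole screen. Inclusion 2 requires good health by history, confirmed with the primary physician; exclusions 6c and 6d remove acute illness and chronic gastrointestinal disease; exclusion 14 lets the investigators exclude any condition that they think poses a risk. This is a single-site study with the insert attached. These are real backstops, and a suspected perforation would in practice be caught. None of them names component hypersensitivity, so the mismatch in wording remains.

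A reader might infer more, and the documents do not support it:

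- *That serious or fatal risk is understated.* Both figures equal the insert's.
- *That each infant's risk is double the quoted rate.* This needs per-exposure rates, which the insert does not state, and equal risk at both feeds, although a reaction to barium at the first is a listed withdrawal reason.
- *That eligibility as a whole admits infants whom the insert rules out.* The gap is shown for exclusion 17 only.
- *That the exclusions contradict the insert on aspiration or reflux.* The insert says "Ingestion of barium is not recommended in patients with a history of food aspiration", but as a precaution, and goes on to allow cautious use. It does not mention reflux.
- *That vomiting, diarrhoea and aspiration pneumonitis are absent from the protocol.* Sections 11.1 and 12 do not list them for the contrast, but both refer to the insert, which does. The consent pages are not available, so what parents are told cannot be judged.
- *That the minimal-risk statement rests on this figure.* Section 12 contains both without linking them.

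**Conclusion.** The point holds in a limited form. As the risk of an allergic reaction of any severity, 1 in 1 million is too low against its cited source by a factor of 4, or 5 if the mild and serious rates are added as separate events. The shortfall is entirely in mild reactions. The expected number of allergic reactions over at most 300 feeds is 0.0012 to 0.0015, against 0.0003 at the stated rate, assuming per-exposure rates and one feed per MRI. The insert's rates are approximate and are taken as printed; the documents do not say whether they apply to infants.

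Separately, exclusion 17 and withdrawal reason 8 are narrower than the contraindication in Appendix 3, with only general or discretionary backstops. Both matters are inconsistencies within the protocol that should be corrected. Neither signals a high hazard or touches the analysis.

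**What to change.** In Sections 11.1 and 12, replace the single allergic-reaction figure with the rates by severity as the insert prints them: mild about 1 in 250,000, serious about 1 in 1,000,000, fatal about 1 in 10,000,000. Reconcile exclusion 17 (Section 4.3) and withdrawal reason 8 (Section 4.4) with the contraindication in Appendix 3. Which clinical rule should apply is for the sponsor to decide.

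The cost is a change of protocol wording, and the stated risk becomes slightly less favourable. No sample size, endpoint or analysis changes.
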